2.1 Purpose

Coronary computed tomography angiography (CCTA) is a frequently performed test for the diagnosis and/or exclusion of coronary artery disease (CAD) in appropriately selected patients¹. The performance of non-contrast computed tomography for the detection and quantification of coronary calcification is typically performed prior to CCTA in an effort to identify significant calcification which may influence subsequent data acquisition during the CCTA. However, performance of calcium scoring adds significant radiation and most coronary calcification is proximal in its location, potentially visualized using a focused non-contrast scan.

The purpose of this study is to prospectively compare the usefulness of a modified non-contrast CT, using a significantly shorter scan length and lower radiation parameters, as compared to standard coronary artery calcium scanning for the detection of coronary calcification that may influence subsequent CCTA performance.

2.2 Research Design:

This is a prospective, randomized single center cohort study to evaluate the diagnostic and clinical impact of a modified versus standard calcium scoring in patients obtaining a coronary CT angiography (CCTA) for the evaluation of symptomatic coronary artery disease.

2.3 Methodology /Technical Approach:

INCLUSION CRITERIA

- 1) Consenting adult patients \geq 50 years of age;
- 2) Suspected but without known prior history of CAD. Prior CAD is defined as a history of myocardial infarction, coronary revascularization or \geq 50% coronary lumen stenosis on prior coronary angiography
- 3) Scheduled for non-emergent clinically indicated coronary CT angiography

EXCLUSION CRITERIA

- 1) Prior coronary bypass graft (CABG) surgery
- 2) Suspicion of acute coronary syndrome (MI or unstable angina)
- 3) Known complex congenital heart disease
- 4) Evidence of ongoing or active clinical instability, including chest pain (sudden onset); cardiogenic shock; unstable blood pressure with systolic blood pressure $<$ 90 mmHg; and severe congestive heart failure (NYHA class III or IV); or acute pulmonary embolism
- 5) Atrial fibrillation
- 6) Abnormal renal function (GFR $<$ 60 ml/min; Creatinine $>$ 1.5 mg/dL)

- 7) Concomitant participation in another clinical trial in which patient is subject to investigation drug or device
- 8) Pregnancy or unknown pregnancy status
- 9) Allergy to iodinated contrast agent
- 10) Contraindications to nitroglycerin
- 11) Unwilling or unable to give consent
- 12) Inability to comply with study procedures
- 13) Prior coronary artery calcium score and/or coronary CT angiogram

DURATION OF STUDY ENROLLMENT: 12 months

SAMPLE SIZE (total enrollment): 175 subjects

3. OBJECTIVES AND SPECIFIC AIMS:

Prior to undergoing CCTA, non-contrast CT scanning of the entire heart is usually performed in adults over 50-years of age in order to assess for the presence and severity of coronary artery calcium. By providing a modified CT scan with a reduced length the same data can be obtained by the imager to ensure a high quality scan while decreasing the patient's overall radiation exposure. Our objectives and specific aims to validate our hypothesis include:

- To assess the impact on CCTA image quality using modified calcium score approach
- To determine the rate of changes in the coronary CT angiography acquisition parameters after evaluation of the modified versus standard calcium scoring scout series. Significant changes in CCTA acquisition include any of the following as compared to recommended CCTA parameters prior to scout CT performance: a change (increase or decrease) in tube current (mA) by 50, any change in tube potential (kV), change to/from retrospectively-gated CCTA, any change in padding (acquisition window), or changing to/from a high definition CT scan acquisition.
- To assess the difference in patient estimated effective radiation exposure (mSv) between the modified versus standard calcium scoring techniques.
- To assess the difference in patient estimated effective radiation exposure (mSv) of the entire CCTA study (plus calcium scoring) between groups.
- .

4. BACKGROUND AND SIGNIFICANCE:

4.1 Literature Review.

Cardiovascular disease is the leading cause of mortality and morbidity in the United States. The impact of coronary disease on our society has prompted increased emphasis on primary prevention. To identify the patients who would benefit the most from primary prevention, such as

the use of HMG-CoA reductase inhibitors, multiple risk factors have been identified that independently correlate with atherosclerotic disease. Of these risk factors, the coronary artery calcium (CAC) score has emerged as a non-invasive independent risk factor for atherosclerotic disease and a tool for the prediction of future cardiac events in asymptomatic patients.² The CAC score has also been identified as having the ability to re-stratify³ and extend to multiple ethnic groups⁴ the predicted risk obtained from the Framingham risk score.

Although the role of the CAC score in the asymptomatic population has been well established its role in a symptomatic patient with suspected coronary artery disease is less clear.

Role of Calcium Scoring Prior to CCTA in the Symptomatic Patient

The most commonly utilized role of the CAC score prior to CCTA is as a gatekeeper to angiography because the specificity and accuracy of the CCTA may vary depending on the amount and location of the coronary calcium⁶. The decrease in sensitivity and specificity is often thought to be due to blooming artifact which can lead to an overestimation in the degree of stenosis or can make the segments un-interpretable on contrast CT angiography. Of note, the data from the Coronary Artery Evaluation Using 64-Row Multidetector Computed Tomography Angiography (CORE-64) study showed that the accuracy and negative predictive value of CCTA to detect a coronary stenosis $\geq 50\%$ in patients referred for ICA is reduced when the CAC score is ≥ 600 ⁷. In a meta-analysis by Abdulla, it suggests that careful pre-angiographic planning needs to occur in patients with CAC score ≥ 400 ⁸ to ensure appropriate study quality and diagnostic accuracy. Furthermore, multiple studies have revealed that high levels of coronary artery calcification is also one of the most important factors associated with a non-diagnostic coronary CTA^{9,10} leading an imager to decide to not proceed with angiography in cases of very high coronary calcification.

Based on the above information, non-contrast CT scanning of the entire heart is usually performed in adults over 50-years of age in order to assess for the presence and severity of coronary artery calcium. This is performed so to identify patients with high degrees of coronary calcium such that the imagers may modify the scan parameters of the subsequent coronary CTA scan in order to optimize image quality and diagnostic accuracy of CCTA. Specific variables that may be adjusted on the subsequent CCTA scan based on the absence or presence and severity of CAC include: tube current (mA), tube potential (kV), use of high-definition scanning, and type of ECG gating/triggering. Of note, the performance of non-contrast CT scan prior to CCTA is typically done using the well-established Agatston method. In this method, the entire heart is scanned using a relatively high tube potential of 120 kV. While this higher tube potential may not be needed to identify calcium, it is a prerequisite in order to calculate an Agatston coronary artery calcium score and is therefore the standard method to perform non-contrast scanning prior to CCTA in our lab and most labs worldwide. Given that the prognostic value of CCTA is superior to calcium scoring, many wonder if the type of non-contrast scan should be modified in order to reduce patient radiation

exposure.

Importantly, it has been demonstrated that the majority of coronary artery calcification occurs in the proximal to mid portions of the coronary arteries¹³. This important fact suggests that a more focused field of view during scout non-contrast CT imaging prior to CCTA may be effective as scanning the entire heart while limiting radiation exposure.

Radiation Exposure

The Society of Cardiovascular Computed Tomography (SCCT) guidelines on radiation dose and dose-optimization strategies in cardiovascular CT states that the imager should attempt to limit the radiation dose to the lowest reasonable level while acquiring as much information as possible in the diagnosis and characterization of a patient's coronary artery disease.

During a cardiac CT examination there are typically three phases: acquisition of a scout view for planning the scan length of the examination, obtaining a low dose non-contrast calcium score, and a contrast-enhanced CT coronary angiography for the evaluation of significant coronary artery stenoses. Typically the scan length of the calcium score is based off of the initial scout. The scan length is defined with the use of anatomic landmarks on an anterior-posterior projection image similar to a chest radiograph. For coronary imaging the scan should typically be started at the mid to lower level of the main pulmonary artery, although a location just below the carina is frequently used and should extend through the apex of the heart.

When performed prior to CCTA, calcium scoring can add anywhere from 1-3 mSv to the total radiation dose⁴. Considering that the mean patient effective radiation dose of a CCTA typically ranges from 2-8 mSv, the performance of a typical calcium score that covers the entire heart and proximal aorta adds proportionally considerable radiation to patients undergoing CCTA. This is of particular importance when the imager is implementing strategies for radiation dose reduction and the calcium score may even double the radiation delivered to the patient. During a CCTA the imaging cardiologist or radiologist may modify scan acquisition modes, x-ray tube potential, x-ray tube current, pitch, scan length and scan field of view dependent upon the method of scanning and the system used to reduce the radiation dose of the angiogram. During calcium scoring, image acquisition parameters are typically not dynamically manipulated but are performed in accordance with standard Agatston scoring parameters.¹⁰ Given the additional radiation of the CAC score to the overall radiation dose of the CCTA there has been some uncertainty of whether CAC scoring should be performed in conjunction with CCTA. However, with this approach the imager would lose the potentially useful information regarding the amount and location of the coronary calcium that could impact decision-making in the acquisition parameters in patients that coronary calcium is likely. The imager may also lose the potentially

important information needed to abort a possibly non-diagnostic exam which would ultimately prevent the patient from receiving unnecessary radiation exposure.

4.2 Scientific Justification. See sections 4.1

4.3 Human Subjects Justification. The use of human subjects is necessary to meet desired endpoints outlined in section 3 to demonstrate the influence of the modified calcium scoring versus the standard calcium scoring for individuals undergoing CCTA.

5. PLAN:

5.1 Study Design

Prospective, randomized single-center cohort study.

5.2 Anticipated Requirements

- a. Facilities: Walter Reed National Military Medical Center
 1. Cardiology Clinic
 2. Cardiovascular Health and Interventional Radiology, Angiography and Recovery [CVHIR]
 3. Radiology Department (CT Section)
- b. Duration of enrollment: 12 months
- c. Budget: no additional budget is needed.

5.3 Subject Population

- a. One hundred seventy-five (175) male and female adult subjects (military health beneficiaries age greater than 50 years) who are clinically referred for CCTA will be eligible for participation.
- b. The Walter Reed National Military Medical Center Cardiology Department and Radiology Departments perform multiple clinically appropriate and indicated coronary CTA studies weekly (approximately 8-12), which will allow for ease of subject recruitment. Although there are other open studies using CCTA in our department there is not a lot of overlap in their requirements and should not prohibit enrollment in our study. This study will enroll both men and women of all ethnic origins aged ≥ 50 years. All subjects will consent for themselves. All patients' participation in this research and subsequent contribution to our medical knowledge notwithstanding, no intent to benefit patients from enrollment is implied or offered. Pregnant women will be excluded from enrollment based on:
 - (1) Verbal admission of pregnant status; OR

(2) Positive urine pregnancy test performed within 7 days of CCTA in subjects not previously known to be pregnant.

5.4 Inclusion and Exclusion Criteria

INCLUSION CRITERIA

- 1) Consenting adult patients \geq 50 years of age;
- 2) Suspected but without known prior history of CAD. Prior CAD is defined as a history of myocardial infarction, coronary revascularization or \geq 50% coronary lumen stenosis on prior coronary angiography
- 3) Scheduled for non-emergent clinically indicated coronary CT angiography

EXCLUSION CRITERIA

- 1) Prior coronary bypass graft (CABG) surgery
- 2) Suspicion of acute coronary syndrome (MI or unstable angina)
- 3) Known complex congenital heart disease
- 4) Evidence of ongoing or active clinical instability, including chest pain (sudden onset); cardiogenic shock; unstable blood pressure with systolic blood pressure < 90 mmHg; and severe congestive heart failure (NYHA class III or IV); or acute pulmonary embolism
- 5) Atrial fibrillation
- 6) Abnormal renal function (GFR < 60 ml/min; Creatinine > 1.5 mg/dL)
- 7) Concomitant participation in another clinical trial in which patient is subject to investigation drug or device
- 8) Pregnancy or unknown pregnancy status
- 9) Allergy to iodinated contrast agent
- 10) Contraindications to nitroglycerin
- 11) Unwilling or unable to give consent
- 12) Inability to comply with study procedures
- 13) Prior coronary artery calcium score and/or coronary CT angiogram

5.5 Study Methodology/Procedures

5.5 Methods:

The FOCUS-CCTA study will be a prospective, randomized single center single cohort study to evaluate the diagnostic and clinical implications of modified scan length calcium scoring versus the standard scan length calcium scoring in CCTAs using a MDCT scanner. Significant diagnostic and clinical implications include the quality of the study in the modified versus standard scan length; changes in the cardiac CT after evaluation of the modified or standard calcium scoring (These changes include: a change in mA by 50, any change in kV, any changes

in padding and changing to high definition.); cancellation of the study and a comparison of the radiation received by each patient.

CCTA Study Design:

Patients who are scheduled for CT coronary angiography for evaluation of clinically suspected coronary artery disease who are fifty years old or older without known coronary artery disease and without a previous calcium score will be prospectively included in this study. The indications for CT coronary angiography will be used in accordance with the ACCF/SCCT/ACR/AHA/ASE/ASNC/NASCI/SCAI/SCMR Appropriate Use Criteria for Cardiac Computed Tomography. Exclusion criteria will include patients who are not able to obtain angiography to include: previous anaphylactoid reaction to iodinated contrast material and renal insufficiency (verified by a renal panel within 30 days of the procedure).

In accordance with standard operating procedures for CCTA (joint Cardiology-Radiology program), patients will arrive to the cardiovascular preparation area (“Prep and Recovery”, Building 9A) and will receive a clinical assessment with vital signs by a physician and nursing staff. Patients without a contraindication to B-adrenergic blocking agents and/or calcium channel blocking agents (will be given a beta-blocker either by oral intake or intravenously prior to the exam to obtain a goal heart rate between 50-65 bpm). Once the patients are within this window they will be escorted to radiology, in accordance with standard CCTA policies. During the preparation time eligible patients will be consented by [name] and will be randomized at that time. The patient’s chart will have an envelope with it that describes which investigational arm the patient will be in. The radiologist and cardiologist will view the card in the envelope after making their initial decision on the parameters for the CCTA.

CT Protocol

All CT examinations will be performed on standard multi-detector CT machines typically utilized for CCTA, in accordance with SCCT guidelines. Prior to any imaging, both the radiologist and cardiologist (non-study personnel) clinically performing the CCTA will fill out a form choosing their initial proposed CCTA acquisition parameters (type of gating, mA, kV, padding, use of high-definition scanning) based on the patient’s age, sex, BMI and achieved pre-scan heart rate, as is typical of all CCTA examinations. Then antero-posterior and lateral topograms of the chest will be obtained to plan subsequent data acquisition, as required for all CCTA examinations. Based on randomization, either a modified or standard calcium scoring series will be performed: Subjects will be randomized in a 1:1 ratio to either modified or standard calcium scoring using a computer program based on random number generation. Assignments will be concealed in sequentially numbered opaque sealed envelopes (SNOSE). The randomization assignment and envelopes will be prepared by a person who is not involved

in the recruitment process or clinical conduct or interpretation of the non-contrast studies or CCTA.

In patients randomized to standard coronary artery calcium scoring, this scan will be performed in usual axial fashion obtained at 70% of the R-R interval using the following parameters: rotation time 0.35 sec; collimation of 64 x 0.625mm; detector coverage of 20.0 mm; axial thickness 2.5; tube voltage, 120 kV and tube current 250mA. The scan length, in accordance with current protocol, will be from 1 cm below the carina through the diaphragms.

In patients randomized to undergo the modified non-contrast CT scan to assess coronary calcification burden, this study will be performed by a radiologist and cardiologist as follows: axial acquisition obtained at 70% of the R-R interval using the following parameters: rotation time 0.35 sec; collimation of 64 x 0.625mm; detector coverage of 20.0 mm; axial thickness 2.5; tube voltage 80kV and tube current 250mA. The scan length will be from 1 cm below the carina to the level beneath the proximal coronary vessels defined as the greatest diameter of the apex of the right atrium. This location has been chosen based off of the experience of the senior cardiologist and radiologist that by choosing this location you will be able to obtain the proximal portion of all the vessels to include the right coronary artery which can be the most difficult to image.

Following completion of the non-contrast CT, the clinically assigned radiologist and cardiologist will determine, based on the information from the non-contrast CT, whether to modify their initial CCTA acquisition parameters or if it is appropriate to continue with CT coronary angiography portion of the exam.

As per standard protocol, prior to initiating the coronary CT angiography, a clinical assessment with vital signs will be performed by a physician and sublingual nitroglycerin spray will be given to all patients for vasodilatation. A timing bolus technique (using 10 cc of iodinated contrast) will be used to determine appropriate timing of the contrast for CCTA, in typical fashion. Following the performance of the timing bolus, CCTA will be performed in accordance with the clinical cardiologist and radiologist parameters, in standard fashion using the injection of iodinated contrast material. The injection protocol will be in accordance with current CCTA lab protocols. Specifically, this will be performed by injecting a bolus of approximately 60 mL of iodinated contrast material (Isovue 370 or Visapaque 320 based on physicians discretion), followed by approximately 50 ml of a 50/50 contrast/saline mixture, then approximately 30 mL of saline solution injected into an antecubital vein via an 18-20 gauge intravenous catheter with an injection rate of 5mL/s by using a power injector.

All CCTA scans will be interpreted using 50% ASIR iterative reconstruction, as per standard CCTA lab protocol.

At the conclusion of the CCTA, the patient, in accordance with standard lab procedures, will be clinically assessed and then transported to the cardiology preparation and recovery area (or inpatient ward, as appropriate. Further care will be in accordance with CCTA standard policies.

CCTA Interpretation and Review:

Non-contrast Computed Tomography (calcium scanning)

Calcium scores performed will be scored in typical fashion using the Agatston scoring method¹¹. The total number of lesions, location (coronary artery), and segment (18-segment model) will be recorded.

Scans performed using the modified calcium scan parameters will be assessed in the following manner:

1. No evidence of coronary calcification
2. Number of segments with visible calcification
3. Severity of calcification: small (<5 mm diameter), moderate (5-10 mm), large (>10 mm or circumferential)
4. Location (segment involved)

In all studies, mean image noise will be assessed as the standard deviation of HU within a 1 cm radius region of interest placed in the middle of the proximal ascending aorta, away from aortic valve and aortic tissue. All calcium scores will be interpreted in a random fashion by two trained readers ([name]). Discrepancies will be resolved by consensus.

CCTA

CCTA studies for both the modified and standard calcium scoring reconstructions will be clinically interpreted by the assigned cardiologist and radiologist, in accordance with standard practice. These results will be provided to the patient and referring provider and reported in the health record in standard fashion. The clinical interpretation team will provide an overall assessment of image quality in the following manner: 1-4 (same scale).

In addition to clinical interpretation, all CCTA studies will be read by two experienced CCTA providers ([name]) while blinded to group allocation. All data sets will be assigned a study ID and will be randomly assigned for interpretation. CCTA interpretations will be performed using all available phases. Coronary arterial segments will be graded for quality (see below), stenosis severity (none; <25%, 25-49%, 50-69% and greater than or equal to 70% or 100%), plaque presence, plaque type (non-calcified, partially calcified, mixed). Differences will be adjudicated by consensus. Interpretation of CCTAs will allow for use of any and/or all image reconstruction methods, including axial slices, multiplanar reformats, and maximum intensity

projections. CCTA image quality will be assessed on a per-segment basis using the 18-segment SCCT model. Image quality will be assessed on a per-segment basis using the following 4-point scale:

Score 1: Non-diagnostic: Impaired image quality that precluded appropriate evaluation of the coronary arteries due to severe motion artifacts, extensive coronary calcifications, severe image noise, or insufficient contrast.

[figure not shown]
Score 2: Adequate: Reduced image quality because of artifacts due to motion, image noise or low contrast attenuation, but sufficient to rule out significant stenosis.

Score 3: Good: Presence of artifacts caused by motion, image noise, coronary calcifications or low contrast, but fully preserved ability to assess the presence of luminal stenosis as well as the presence of calcified and non-calcified coronary atherosclerotic plaque.

[figure not shown]
Score 4: Excellent: Complete absence of motion artifacts, strong attenuation of vessel lumen and clear delineation of vessel walls, with the ability to assess luminal stenosis as well as plaque characteristics.

The overall patient study quality will be determined by the mean of these scores after reaching consensus. In addition, CCTA signal (mean CT number, Hounsfield unit [HU]), noise (standard deviation in HU) and contrast/noise

The two readers will measure the signal and noise in the aortic root and each of the proximal coronary arteries with the mean of the readers used for comparisons. The contrast to noise will also be evaluated (difference of the mean arterial/aorta signal divided by the mean noise). *✓ this*

Flow sheet

5.5.1 Describe when, where and how the study subjects will be identified and recruited.

Patients seen in Cardiology clinic who are deemed by their referring provider(s) as potential candidates for the FOCUS-CCTA trial will be referred to [name] (Research Nurse, Associate Investigator) to determine their eligibility, there will be no screening process prior to identification by their primary cardiologist to identify potential candidates. The patient can choose to meet with [name] in person or be contacted via a phone call to determine eligibility and enrollment based on inclusion/exclusion criteria. If the patient is not eligible for enrollment he/she will be thanked for his/her interest and willingness to participate and will be directed back to the referring provider for continued care. If the patient is deemed eligible he/she will be requested to obtain the appropriate labs if not already documented, complete informed consent and HIPAA Authorization for enrollment and a de-identified random subject number will be generated.

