5.8. Endpoints

Primary

The measurement of quality in comparison of the modified versus non-modified CCTA using a qualitative (four point scale and measure above) and quantitative (CCTA signal, noise, contrast to noise ratio) score.

Secondary

1. Any changes in the cardiac CT after evaluation of the modified or standard calcium scoring. These changes include: a change in mA by 50, any change in kV, any changes in padding and changing to high definition
2. The measurement of radiation exposure as DLP/milli-sieverts in comparison of the modified versus standard calcium scoring.
3. The measurement of radiation exposure difference measured as DLP/milli-sieverts of the entire CCTA study on the modified versus standard calcium scoring.
4. Whether the imager cancels the study based off of the modified or standard calcium scoring.

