6.3 Actions to Minimize Risks

a. Safety Monitoring Plan

Safety of participants is of primary concern to study investigators, and every effort to avoid adverse events (AE) will be made. An AE will be defined as any unfavorable and unintended sign, symptom, or disease temporally associated with the study procedures, whether or not considered related to the procedure. Only symptoms/signs that begin, increase in frequency or worsen in severity after the procedure start will be considered as AEs. Any asymptomatic change from baseline such as results from diagnostic procedures (renal function or vital signs that is clinically significant (e.g., requires diagnostic or therapeutic intervention beyond confirmation alone) will be considered an adverse event.

CCTAs performed for this study are clinically indicated as designated by their primary cardiologist, and while risk is minimal for CCTA performance, all potential safety efforts will be employed. CCTA examination will be prescribed, performed and under the direct supervision of a study physician. Adverse effects of any CCTA exam (not specific to the choice of tube voltage) may include contrast reaction, impairment of renal function (by contrast dye) and exposure to small amounts of ionizing radiation. Patients will be screened for a history of contrast reaction. If a patient develops a contrast reaction, a fully equipped crash cart and ACLS-trained nurses will be present to administer appropriate care. Impairment of renal function will be avoided by the use of an iso-osmolar contrast agent as well as preferred selection for performance of CCTA. CCTAs will be performed by prospective ECG triggering as a first-line mode, given its merits for lowering radiation dose. Estimated radiation dose for prospectively ECG triggered scans is between 2-8 mSV.

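### The contrast product is left to discretion and need not be chosen before the allocation card is opened, so an arm-aware choice could shift or mask the primary signal and contrast-to-noise comparison

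*Combined protocol and SAP*

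**What the plan says.** Section 5.5 sets this sequence:

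- Before any imaging, the clinical radiologist and cardiologist "will fill out a form choosing their initial proposed CCTA acquisition parameters (type of gating, mA, kV, padding, use of high-definition scanning" and so on.
- "The radiologist and cardiologist will view the card in the envelope after making their initial decision on the parameters for the CCTA".
- The arm-specific non-contrast scan follows. The same pair then decides whether to change their initial settings and whether to go on to the CCTA.
- The injection is described after that, at 5 mL/s and under current lab protocols. The main bolus, roughly 60 mL, uses "iodinated contrast material (Isovue 370 or Visapaque 320 based on physicians discretion". A half-strength phase of roughly 50 mL comes next, and saline last.

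The primary endpoint in section 5.8 includes a "quantitative (CCTA signal, noise, contrast to noise ratio) score". The 4-point scale in section 5.5 also depends on opacification: its lowest grade lists "severe image noise, or insufficient contrast" among its causes, and the grades above it also refer to contrast or attenuation.

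The CT Acquisition Data Sheet in section 5.5.5 captures gating type, padding, tube current and tube voltage before and after the calcium scan. It captures contrast type, iodine concentration and volume once. Section 5.7.1 compares signal/noise by a two-sample t-test without covariates. The ordinal regression in section 5.7.3 concerns the quality score only and does not name the contrast product, although its covariate list is open-ended.

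On safety, section 6.3 says: "Impairment of renal function will be avoided by the use of an iso-osmolar contrast agent".

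**The concern.** The two study readers are blinded, but the operators who acquire the CCTA are not. Blinded reading protects the scoring. It cannot undo a difference in how the images were made.

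The product is an acquisition choice that affects the measured outcome, yet it is neither committed before the card is opened nor counted as a change afterwards. A switch of product is not among the Aim 2 changes in sections 3, 5.7.1 and 5.8. With a single contrast entry on the data sheet, a switch made after the calcium scan would look the same as a choice made at the outset.

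Two errors are possible. If the higher-concentration product were used more often in the modified arm, a real loss of signal could be hidden. Section 5.7.2 frames image quality as non-inferiority, so that error favours the new method. If the imbalance ran the other way, a loss could appear that the calcium scan did not cause.

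**Working it through.** **The plan's own figure.** Section 5.7.2 gives 80% power for the 4-point score with 79 per group, SD 1.10, margin 0.49, assumed means 3.20 and 3.15, and one-sided alpha 0.05.

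- SE = 1.10 × √(2/79) = 0.175.
- (0.49 − 0.05)/0.175 = 2.514, and 2.514 − 1.645 = 0.869.
- Power = Φ(0.869) = 80.8%, or 80.5% with the noncentral t.

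The figure reproduces. The plan states no SD or power for signal or contrast-to-noise, so what follows needs assumptions.

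**Inputs from section 5.5.** Labels 370 and 320; about 60 mL, then about 50 mL of a half-contrast mix; 5 mL/s. From section 5.7.2: 79 per group.

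**Assumptions.** The labels are mg iodine/mL. Arterial signal is proportional to iodine. The between-patient coefficient of variation (CV) of signal is 15% to 30%. The same percentages apply to a signal/noise ratio only if noise does not depend on the product.

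**Iodine difference.**

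- 370/320 = 1.156 (15.6% more); 320/370 = 0.865 (13.5% less).
- Rate: 5 × 0.370 = 1.85 g/s against 5 × 0.320 = 1.60 g/s.
- Main injection: 60 + 50/2 = 85 mL, giving 85 × 0.370 = 31.5 g against 85 × 0.320 = 27.2 g.

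**Effect of unequal use.** Let d be the between-arm difference in the proportion given one product.

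- Relative shift in mean signal = (1 − 320/370) × d = 0.135 × d.
- SE of the relative difference = CV × √(2/79): 2.39% at CV 15%, 4.77% at CV 30%.
- False-positive risk is that of a two-sided 5% test when the calcium scan has no effect.
- Remaining power is for a true deficit that would otherwise be detected with 80% power, with the shift in the masking direction.

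| d | Shift | Shift in SEs (CV 30% to 15%) | False-positive risk | Remaining power |
|---|---|---|---|---|
| 10 points | 1.4% | 0.28 to 0.57 | 5.9% to 8.7% | 71% to 61% |
| 20 points | 2.7% | 0.57 to 1.13 | 8.7% to 20.5% | 61% to 39% |
| 30 points | 4.1% | 0.85 to 1.70 | 13.6% to 39.7% | 50% to 20% |

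**Chance as a benchmark.** If the choice were independent of arm and split evenly, the SD of d would be √(0.25 × 2/79) = 0.080, or 8 points. A 10-point difference is therefore unremarkable by chance. Chance imbalance adds noise rather than systematic bias; the table matters for imbalance that arises because the operators know the arm.

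**The case against.** Several stronger readings are tempting, and the documents do not support them.

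- *The product is chosen by operators who already know the arm.* A reader might infer this from the order of section 5.5. That section times the injection, not the choice of product, which may well be made earlier. What stands is that nothing requires it to be.
- *Volume is discretionary too.* The discretion attaches to the product. Volumes and rate are given as lab protocol, though approximately.
- *The form locks the settings, and contrast escaped the lock.* The form holds "initial proposed CCTA acquisition parameters (type of gating, mA, kV, padding, use of high-definition scanning" and the like as proposals that may be changed after the scan. It is the Aim 2 baseline and locks nothing.
- *Any switch is bias.* Aim 1 asks how the modified approach affects image quality, and operators are expected to act on what the scan shows. A switch prompted by a scan finding is arguably part of that approach. Only a switch prompted by knowing the arm is clearly bias, and the present data sheet cannot tell them apart.
- *A shift of a definite number of HU follows.* The documents give no HU level. An assumed 400 HU would make the products differ by 54 HU (400 × 0.135) or 62.5 HU (400 × 0.15625), depending on which product it describes. No imbalance in use is documented either.
- *Sections 5.5 and 6.3 flatly contradict each other.* Section 5.5 leaves two products open, while section 6.3 relies on one class of agent. Neither gives an osmolality, so the documents support a request to reconcile and no more.

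It is also fair that section 4.1 does not list contrast among the settings adjusted for calcium, and that the operators are described as non-study personnel. Both make arm-driven choice less likely. Product use by arm could already be tabulated from the recorded data. These points lower the probability of harm, but they do not close the route.

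**Conclusion.** The concern holds as a possibility that the plan leaves open, not as a demonstrated bias. The product is discretionary, absent from the form completed before the card is opened, recorded once, and relevant to both parts of the primary endpoint.

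The size cannot be known in advance. Under the stated assumptions, a 10-point imbalance in use matters little for false-positive risk and is within what chance would produce, although it would cost some power if it ran in the masking direction. From about 20 points, a shift of about 3% in mean signal, the effect on the test becomes material. These figures concern signal. No effect on the 4-point score, the image-quality measure used for the power calculation, can be derived from the documents. The change is worth making because it costs almost nothing.

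**What to change.** 1. Add the planned contrast product to the section 5.5 form, so that it is committed before the card is opened.
2. On the section 5.5.5 data sheet, record any later change of product beside the other before-and-after items, with its reason: scan finding, clinical need or other. Clinically needed changes stay allowed.
3. Report planned and actual product by arm.
4. Pre-specify a sensitivity analysis of signal and contrast-to-noise adjusted for the planned product. Because that is fixed before the arm is known, the adjustment improves precision and corrects chance imbalance. It does not remove bias from later switching; the early commitment and the recorded switches address that.
5. Reconcile sections 5.5 and 6.3 on the agents to be used. This review takes no view on which agent is right.

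The cost is one extra field on an existing form, the added change record, a slightly earlier commitment by the operators and one extra analysis. The sample size does not change.
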